#### **6.4.2 Secondary Efficacy Analyses**

Secondary efficacy endpoints are OS, ORR, DOR, and PFS assessed by independent review.

OS is defined from randomization until death from any cause. For patients who are alive at the time of analysis data cutoff, OS time will be censored at the last date the patient was known to be alive. Survival time for patients with no post-baseline survival information will be censored on the date of randomization.

The final analysis of ORR will take place at the time of final analysis of PFS. BORR will be assessed by the investigator according to the RECIST v1.1. Confirmed ORR is defined as the total number of patients whose best overall response is CR or PR divided by the population evaluable for ORR. Confirmation of response (partial response or complete response) will be done no earlier than 28 days. In the case of stable disease, measurements must have met the stable disease criteria at least once after study entry at a minimum interval not less than 6 weeks. Treatment difference in BORR will be tested using a chi-square test with Schouten correction, and a 95% Hauck-Anderson CI will be calculated for the difference in BORRs between treatment groups. In addition, a 95% Clopper-Pearson CI will be calculated for the BORR.

DOR is defined as the interval between the date of the earliest qualifying response and the date of progressive disease or death for any cause. This will be calculated only for patients who had a confirmed overall response of CR or PR. Median duration of response will be estimated using the Kaplan-Meier method, and the 95% CI will be calculated using the method of Brookmeyer and Crowley (1982). Since the

determination of DOR is based on a non-randomized subset of patients, formal hypothesis testing will not be performed on this endpoint.

## 6.5 SAFETY ANALYSES

Safety will be assessed through summaries of all adverse events, including serious adverse events, adverse events of special interest, and adverse events leading to discontinuation of study treatment.

***Adverse events will be summarized using MedDRA by mapped term, appropriate thesaurus level, and toxicity grade.*** Adverse events will be graded by the investigator using NCI CTCAE v4. The following safety parameters will be summarized by treatment arm:

- All adverse events
- All adverse events leading to discontinuation of study treatment
- All deaths
- Serious adverse events
- Adverse events of special interest (see Section 5.2.3 for a list of adverse events of special interest for this study)

In addition, exposure to study treatment (vemurafenib, cobimetinib, placebo), including cumulative dose and treatment duration, will be summarized by treatment arm. Selected laboratory data will be summarized by treatment arm and toxicity grade (NCI CTCAE v4.0).

## 6.6 PHARMACOKINETIC ANALYSES

Summary statistics will be used as appropriate to perform the descriptive analysis of the plasma concentrations of vemurafenib and cobimetinib. Cobimetinib and vemurafenib concentrations will be measured as shown in [Appendix 2](#). Cobimetinib and vemurafenib plasma concentration versus time data, together with information on dosing and patient characteristics, will be pooled and analyzed using a pop PK analysis approach. Nonlinear mixed-effect modeling will be used for the estimation of pop PK parameters for cobimetinib and vemurafenib. Covariates such as patient demographics (e.g., age, sex, body size), total protein, serum albumin, liver function tests (e.g., AST, ALT, ALP), and serum creatinine will be tested for significance on PK parameters of interest. The PK data in this study might be pooled with PK data from other studies.

The PK data will be combined with the safety (e.g., QTc) and efficacy (e.g., PFS) data for exposure–response modeling as data permit. PK and PK–pharmacodynamic analyses may be reported in separate stand-alone reports. Additional analyses may be explored as warranted by the data.

## **6.7 PATIENT-REPORTED OUTCOMES**

Quality of life, as measured by EORTC QLQ-C30, will be evaluated for patients with a baseline assessment and at least one post-baseline QLQ-C30 assessment that generate a score. Total QLQ-C30, each domain score (e.g., physical functioning, role functioning, emotional functioning, cognitive functioning, social functioning), as well as symptom scales, will be examined at baseline, and change from baseline for each timepoint by use of descriptive statistics.

Repeated measures mixed-effects models will be the primary models for the formal comparison of the QLQ-C30 multiple-item subscale scores between treatment arms. Each model will have a term for intercept, a term for a linear time trend term (in weeks), a term for treatment group, and a term for treatment-by-time interaction. Repeated measures over time will be accounted for by unstructured covariance structure (using the REPEATED statement in SAS® PROC MIXED).

Health economic measures, as assessed by the EQ-5D, will be evaluated for patients with a baseline assessment and at least one post-baseline EQ-5D assessment that generate a score. Scores at baseline and change from baseline scores for each timepoint will be quantified with descriptive statistics.

Following approval of v5 of the protocol, PRO data will no longer be collected.

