### **3.3.7 Rationale for Health-related Quality of Life Assessment and Health Economic Assessment**

The HRQL EORTC QLQ-C30 is included to characterize the impact of treatment on patients while receiving and following vemurafenib and cobimetinib exposure. These data should allow for quantification of the health economic impact of these treatments, given the externally validated data generated from the EQ-5D self-reported questionnaire. The collection of this type of data will provide greater insights for both the medical and patient communities to understand patient-reported value and quality of life when exposed to the combination of vemurafenib and cobimetinib treatments.

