#### **4.5.1.9 Patient Reported Outcomes**

Following approval of v5 of the protocol, PRO data will no longer be collected.

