**Table 9 Dose Level Reductions**

Dose reduction	Vemurafenib	Cobimetinib
1 dose level	720 mg BID	40 mg QD
2 dose levels	480 mg BID	20 mg QD

BID=twice daily; QD=once daily.

Dose modifications, interruptions, and delays of vemurafenib and/or cobimetinib study treatment should be made on the basis of the guidelines provided in [Table 10](#). The dose modification guidelines are not intended to replace clinical judgment or dictate care of individual patients. Dose reduction of each study drug is independent of the other study drug. Dose re-escalation is not allowed.

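### The formal QLQ-C30 model has no term for the baseline score that every analysed patient must have, which costs precision; its straight line in weeks misplaces an early difference only if baseline is itself a response

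*Protocol*

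**What the plan says.** Section 6.7 gives the model its role: "Repeated measures mixed-effects models will be the primary models for the formal comparison of the QLQ-C30 multiple-item subscale scores between treatment arms". It then lists the mean structure: "Each model will have a term for intercept, a term for a linear time trend term (in weeks), a term for treatment group", followed by a treatment-by-time interaction. On the covariance it says "Repeated measures over time will be accounted for by unstructured covariance structure". Neither a baseline-score term nor a categorical visit term appears.

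On the analysed patients, quality of life "will be evaluated for patients with a baseline assessment and at least one post-baseline QLQ-C30 assessment that generate a score". Baseline scores and "change from baseline for each timepoint by use of descriptive statistics" are summarised but have no stated place in the model.

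The section does not say whether the modelled response is post-baseline scores, change from baseline, or all scores with baseline at week 0. It does not say which contrast is the test.

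Section 3.3.7 says the QLQ-C30 "is included to characterize the impact of treatment on patients while receiving and following vemurafenib and cobimetinib exposure". Section 4.5.1.9 records that after version 5 "PRO data will no longer be collected", and the current schedule of assessments has no quality-of-life visits.

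**The concern.** A baseline score is usually the strongest predictor of later scores on the same scale. Here it exists for every analysed patient, so using it as a covariate loses nobody. Leaving it out of the only formal between-arm QLQ-C30 comparison widens the interval for no gain.

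The straight line raises a second question. Randomisation makes the true arm difference zero at baseline. If baseline is one of the modelled responses, a difference that appears early and then holds is a step, and one line per arm cannot follow a step. The unstructured covariance does not help, because it leaves the mean linear.

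The stakes are modest. Quality of life is a separate objective, outside the primary and secondary efficacy objectives, and no power, significance level or decision is attached to it.

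**Working it through.** The protocol gives no effect size, SD, power or visit schedule for the QLQ-C30, so there is no figure to reproduce.

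**Assumed inputs.** Visits at weeks 0, 4, 8, 16, 24 and 32; SD 20; 200 patients per arm (about 500 are randomised 1:1); correlation ρ of 0.3, 0.5 or 0.7, either exchangeable or AR(1) per visit step; a true difference of 5 points at every visit from week 4; known covariance; two-sided 5% tests.

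**1. Precision of the visit-averaged difference.** The variance of an arm difference at one visit is D = 2 × 20² / 200 = 4. With five post-baseline visits and exchangeable correlation:
- post-baseline scores: D(1 + 4ρ)/5
- with baseline as covariate: the above − Dρ²
- change from baseline: D(1 + 4ρ)/5 − 2Dρ + D

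At ρ = 0.5 these are 4 × 3/5 = 2.40, then 2.40 − 1.00 = 1.40, then 2.40 − 4 + 4 = 2.40.

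For AR(1) with ρ = 0.3, the post-baseline variance is (4/25)[5 + 2(4ρ + 3ρ² + 2ρ³ + ρ⁴)] = 0.16 × 8.064 = 1.290. The mean correlation with baseline is (ρ + ρ² + ρ³ + ρ⁴ + ρ⁵)/5 = 0.0855. The adjusted variance is 1.290 − 4 × 0.0855² = 1.261, and the change-score variance is 1.290 − 8 × 0.0855 + 4 = 4.606.

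| Correlation | Post-baseline | Baseline-adjusted | Change | Cut by adjusting post-baseline scores | Change ÷ adjusted |
|---|---|---|---|---|---|
| Exchangeable 0.3 | 1.76 | 1.40 | 3.36 | 20% | 2.40 |
| Exchangeable 0.5 | 2.40 | 1.40 | 2.40 | 42% | 1.71 |
| Exchangeable 0.7 | 3.04 | 1.08 | 1.44 | 64% | 1.33 |
| AR(1) 0.3 | 1.29 | 1.26 | 4.61 | 2% | 3.65 |
| AR(1) 0.5 | 1.78 | 1.63 | 4.23 | 8% | 2.60 |
| AR(1) 0.7 | 2.46 | 1.86 | 3.36 | 24% | 1.80 |

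A 64% cut means that the unadjusted variance is 3.04/1.08 = 2.81 times the adjusted one.

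Power follows from z = 5/√variance. At exchangeable 0.5, 5/√2.40 = 3.23 gives Φ(3.23 − 1.96) = 90%, and 5/√1.40 = 4.23 gives 99%. Over the table, power is 82-99% without baseline and 96% to over 99% with it. The stated linear model's contrast at the mean visit time also has 82-99%. Adding baseline to that linear model gives 98% to over 99%, so the gain comes from the covariate and not from the form of time.

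**2. Shape, post-baseline scores only.** A constant difference is a horizontal line. The fit returns 5 with slope 0, so there is no bias.

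**3. Shape, baseline as the week-0 response.** The true differences are 0, 5, 5, 5, 5, 5. Under exchangeable correlation the generalised least-squares fit of the difference equals ordinary least squares:
- mean week = 84/6 = 14; mean difference = 25/6 = 4.17
- sum of squares of weeks = 196 + 100 + 36 + 4 + 100 + 324 = 760
- cross-product = 5 × (−10 − 6 + 2 + 10 + 18) = 70
- slope = 70/760 = 0.092 points per week (truth 0 after week 4)
- week 0: 4.17 − 14 × 0.092 = 2.88 (truth 0)
- week 4: 2.88 + 4 × 0.092 = 3.25 (truth 5)
- week 32: 5.82 (truth 5)

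Under AR(1) with ρ = 0.3, 0.5, 0.7 the fit gives 2.51, 2.20, 1.82 at week 0; 2.91, 2.62, 2.25 at week 4; and 5.77, 5.63, 5.30 at week 32.

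**4. Sensitivity.** With other assumed schedules (5, 8 or 13 assessments ending at week 24, 32 or 48), the unadjusted variance is 1.12-3.09 times the adjusted one, and change scores give 1.32-2.93 times. A 10-point step with baseline as a response is fitted as 1.6-7.3 at week 0 and 2.9-7.6 at the first later visit. If assessment stops at progression, with the planned 6- and 11-month medians, power for the average difference is 80-97% unadjusted and 92-99% adjusted.

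**The case against.** Several stronger readings are tempting, and the documents do not support them.

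- *The formal comparison is biased.* This needs baseline to be the week-0 response. Section 6.7 never says so, and with post-baseline scores a constant difference is unbiased.
- *The early confidence intervals are wrong.* With baseline in the response, the nominal 95% interval at week 4 would cover the truth 63-83% of the time under the assumptions above. But section 6.7 plans no model-based estimate at week 4. It gives per-timepoint change only descriptively, and those summaries do not depend on the line.
- *The model has no power for a constant difference.* The treatment-by-time term alone has 5% power in the post-baseline case, but nothing says that term alone is the test. The joint test of treatment and treatment-by-time has 73-98% (post-baseline only) or 69-96% (baseline in the response).
- *A step is the expected shape.* Toxicity is handled by interruption and reduction, and "Dose re-escalation is not allowed". That makes a step or a fading difference conceivable, but the protocol gives no quality-of-life trajectory.

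The strongest general objection is that response, contrast and covariates are commonly left to a SAP, which is not shown. For the response and the contrast that is fair, and their absence is no fault here. The mean structure is different: the protocol writes the terms out and fixes the covariance as well, so a SAP with other terms would depart from the listed model. It is also true that the section does not forbid further covariates, that linear time is a conventional choice, and that the precision loss can be as small as 2%.

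**Conclusion.** The point holds as a minor one. The protocol's listed model for its only formal QLQ-C30 comparison leaves out a baseline score that the analysis population is defined to have. Both readings without baseline as a response lose precision to this omission, and the loss disappears on the post-baseline reading only as the correlation between baseline and later scores approaches zero. The misplaced early difference is conditional on the third reading and should be reported only as conditional. Linear versus categorical time is partly a trade-off and not an error in itself.

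Confidence is high that the term is missing and in the direction of the effect. It is moderate on size, because the schedule, SD, correlation, effect and number of evaluable patients are all assumed.

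**What to change.** Keep the stated model. Beside it, report a supplementary repeated-measures model, labelled post hoc, with baseline score, baseline-by-visit, visit as a category, treatment and treatment-by-visit. Give the difference at each visit and the visit-averaged difference, each with its confidence interval. State which scores are the response in the linear model, and do not read its treatment-by-time term alone as the between-arm comparison.

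No new data are needed. Collection has ended and the final survival analysis is done, so the model can only be a supplement. It needs a few more mean parameters; the unstructured covariance already treats visits as discrete.

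Categorical visits have a price. For a difference growing linearly to 10 points at week 32, the treatment-by-visit test (4 df) has 77% to over 99% power, against 91% to over 99% for the linear treatment-by-time term. For a fading difference (5 points at weeks 4 and 8, 2.5 at week 16, then 0), the visit average has only 45-67%. The joint test over visits keeps 71-99%, about the same as the linear joint test on post-baseline scores (69-99%). The per-visit differences should therefore always stand beside the average.

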## **6.8 BIOMARKER ANALYSES**

Biomarker analyses will be provided in a separate report. Descriptions of biomarker analyses will be provided in a Biomarker Analysis Plan.

## **6.9 INTERIM ANALYSES**

### **6.9.1 Interim Efficacy Analyses of Primary Endpoint**

No interim analyses of the primary endpoint (PFS) will be performed.

### **6.9.2 Analysis of Overall Survival**

The OS analyses plan for this study protocol (v5) and the statistical analysis plan (SAP) have been revised. The study will incorporate 2 OS analyses (1 interim and 1 final analysis). The first OS interim analysis was performed at the time of the primary PFS analysis (16 months after the first patient was randomized). The originally planned final analysis for OS at 385 events is anticipated to occur in the second quarter of 2017. The rapid development of other potentially effective therapies for patients with metastatic melanoma provides more treatment options for patients following disease progression, which may potentially confound the OS benefit of vemurafenib + cobimetinib in future OS analyses. Therefore, in order to minimize this potential impact while maintaining a statistically robust evaluation of the OS benefit associated with the combination, the protocol-defined OS analyses have been revised.

The revised plan for OS analyses is to perform the final OS analysis at approximately 250 deaths without further interim analyses. The type 1 error rate would be strictly controlled at the 0.05 level by the continued use of the Lan-DeMets implementation of the O'Brien-Fleming use function as pre-specified in the original protocol and SAP.

The final OS analysis will be performed after the occurrence of approximately 250 deaths (projected to occur at approximately 31 months after the first patient was randomized). The Lan-DeMets implementation of the O'Brien and Fleming use function will be used to control the overall type I error for the OS comparison at a 2-sided, 0.05 significance level. [Table 12](#) summarizes the assumptions and characteristics of the interim and final analyses for OS.

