### Analysis of overall survival:

The OS analyses plan for this study protocol (v5) and the statistical analysis plan (SAP) have been revised. The study will incorporate 2 OS analyses (1 interim and 1 final analysis). The first OS interim analysis was performed at the time of the primary PFS analysis (16 months after the first patient was randomized). The originally planned final analysis for OS at 385 events is anticipated to occur in the second quarter of 2017. The rapid development of other potentially effective therapies for patients with metastatic melanoma provides more treatment options for patients following disease progression, which may potentially confound the OS benefit of vemurafenib+cobimetinib in future OS analyses. Therefore, in order to minimize this potential impact while maintaining a statistically robust evaluation of the OS benefit associated with the combination, the protocol-defined OS analyses have been revised.

The revised plan for OS analyses is to perform the final OS analysis at approximately 250 deaths without further interim analyses. The type 1 error rate would be strictly controlled at the 0.05 level by the continued use of the Lan-DeMets implementation of the O'Brien-Fleming use function as pre-specified in the original protocol and SAP.

The final OS analysis will be performed after the occurrence of approximately 250 deaths (projected to occur at approximately 31 months after the first patient was randomized). The Lan-DeMets implementation of the O'Brien and Fleming use function will be used to control the overall type I error for the OS comparison at a 2-sided, 0.05 significance level.

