#### 1.4.4 Primary and Final Analysis of Study GO28141

Primary analysis of study GO28141 was conducted with a data cutoff of 9 May 2014 (Larkin et al. 2014). At the time, median PFS for the 247 patients enrolled in the vemurafenib + cobimetinib arm was 9.9 months versus 6.2 months for the 248 patients enrolled in the vemurafenib + placebo arm (hazard ratio: 0.51; 95% CI: 0.39, 0.68). Similarly objective response rate (ORR) was 68% versus 45% ( $p < 0.0001$ ) for vemurafenib + cobimetinib versus vemurafenib + placebo. Final analysis of OS occurred with a data cutoff of 28 August 2015. At the time, median OS was 22.3 months for patients treated with vemurafenib + cobimetinib versus 17.4 months for patients treated with vemurafenib + placebo (hazard ratio: 0.70; 95% CI: 0.55, 0.90). Overall, safety was consistent with a positive benefit-risk profile for the combination.

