**Table 12 Assumptions and Characteristics of the Interim and Final Analyses for Overall Survival**

Assumptions	Findings
HR targeted	0.70
Targeted median (vemurafenib+placebo)	15 months
Targeted median (vemurafenib+cobimetinib)	21.4 months
Projected enrollment period	12.7 months
First interim OS (to be performed at time of final PFS analysis)	
Estimated cutoff date a	16 months after FPI
Projected number of events (% of final events)	85 c (34%)
Projected MDD b (p-value)	0.45 (<0.000242)
Final OS	
Number of events (% of final events)	250 (100%)
Estimated cutoff date a	31 months after FPI
Projected MDD b (p-value)	0.78 (<0.0499)
Power	80%
$\alpha$ level (2-sided)	0.05

FPI = first patient in; HR = hazard ratio; MDD = minimally detectable difference; PFS = progression free survival; OS = overall survival.

a Estimated data cutoff time from study enrollment date. Analysis results will be available after data cleaning.

b The largest observed HR that is projected to be statistically significant.

c The actual number of events observed at the interim analysis in July 2014

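### Does cutting the final OS target from 385 to 250 deaths after the interim undermine the claim that OS type I error is strictly controlled?

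*Protocol*

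**What the plan says.** Section 6.9.2, repeated almost word for word in the synopsis, sets out the sequence.

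- The interim had already happened: "The first OS interim analysis was performed at the time of the primary PFS analysis". Table 12, footnote c, describes its 85 deaths as "The actual number of events observed at the interim analysis in July 2014".
- The former target: "The originally planned final analysis for OS at 385 events is anticipated to occur in the second quarter of 2017".
- The new target: "The revised plan for OS analyses is to perform the final OS analysis at approximately 250 deaths without further interim analyses".
- The reason: newer treatments for metastatic melanoma could blur a later OS comparison.
- The assurance: "The type 1 error rate would be strictly controlled at the 0.05 level by the continued use of the Lan-DeMets implementation" of the O'Brien-Fleming spending function, which the section says was already in the original protocol and SAP.

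Table 12 gives boundaries of p<0.000242 (HR 0.45) at 85 deaths and p<0.0499 (HR 0.78) at 250, with 80% power for HR 0.70.

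On data access, Section 3.5 keeps by-arm summaries from the sponsor until the primary efficacy results are formally reported. Section 4.2 keeps the sponsor blinded to treatment assignment until the final OS analysis is complete. Section 1.4.4 says "Primary analysis of study GO28141 was conducted with a data cutoff of 9 May 2014" and gives PFS and response by arm from that cutoff, but no interim OS result. It then says "Final analysis of OS occurred with a data cutoff of 28 August 2015".

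**The concern.** Spending functions let the number and timing of looks vary, on condition that the choice does not depend on the observed treatment effect. Here the maximum information fell by 35% (135 of 385 deaths) after an OS look. Keeping the same function says which function is used. It does not say who chose 250 deaths or what they had seen.

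If those who chose it knew the interim OS result, a final threshold of 0.0499 would be more lenient than the original design whenever the interim was favourable, and the unconditional assurance would be wrong. OS is the first-listed secondary endpoint, so its error rate matters.

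Table 12 also shows the July 2014 look against a boundary computed on 250 deaths, although the planned total at that time was 385.

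**Working it through.** **Inputs.** 85, 250 and 385 deaths, two-sided alpha 0.05, HR 0.70 (Sections 6.1.2 and 6.9.2, Table 12), and 1:1 allocation (Section 3.1). Not in the protocol: the interim HR and any further looks in the 385-death plan. The comparisons with 385 deaths assume a single interim unless stated otherwise.

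**1. Reproduce Table 12.** Two-sided spending is α(t) = 4[1 − Φ(2.2414/√t)], and an HR boundary is exp(−2c/√d).

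- Interim: t = 85/250 = 0.34; 2.2414/0.5831 = 3.844; α = 0.000242. The critical z is 3.670, and the HR is exp(−2 × 3.670/√85) = 0.451.
- Final: the bivariate normal with correlation √0.34 gives z = 1.9607, p = 0.0499, HR = exp(−2 × 1.9607/√250) = 0.780.
- Power: Φ(0.3567 × √250/2 − 1.9607) = Φ(0.859) = 80.5%.

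All agree with the table.

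**2. The same look under the 385-death plan.** t = 85/385 = 0.221 gives p = 0.0000037 and HR 0.366. Table 12's interim boundary is therefore about 66 times looser. This does not inflate the error, because the final critical value takes the spending into account.

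**3. Error if the cut was independent of interim OS.** Two-sided 0.0500 if the interim is judged on 85/250. Two-sided 0.0499 if it was judged on 85/385 and the final uses p<0.0499. The claim holds either way.

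**4. Error if the cut was not independent.** The conditional error for a final at d deaths is CE_d(z) = 1 − Φ[(c_d − z√(85/d))/√(1 − 85/d)], with c = 1.9607 at 250 and 1.9600 at 385.

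- The two are equal at z = 1.041, which is an interim HR of exp(−2 × 1.041/√85) = 0.798.
- At an assumed interim HR of 0.70 (z = 1.644): CE250 = 1 − Φ(1.233) = 0.109 and CE385 = 1 − Φ(1.345) = 0.089, so 250 deaths is the more lenient.
- At an assumed interim HR of 0.90: 0.019 against 0.025, so 250 deaths is the stricter.
- Taking the larger of the two at every z and integrating under the null gives 0.0281 one-sided, or about 0.056 two-sided.
- If any target from 90 to 385 deaths (in steps of 5) could be picked to suit the interim, the bound is about 0.045 one-sided.

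**5. The reported result.** Section 1.4.4 gives HR 0.70 (0.55 to 0.90). The SE is ln(0.90/0.55)/3.92 = 0.1256, so z = 0.3567/0.1256 = 2.84 and p is about 0.0045.

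- Thresholds at 250 deaths that preserve the 385-death conditional error are p<0.024, 0.035, 0.040, 0.050 and 0.060 for assumed interim HRs of 0.52, 0.65, 0.70, 0.80 and 0.90.
- Treating 250 deaths as an interim of the 385-death plan (64.9% information) gives p<0.0108.

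The reported p-value is below all of these.

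**The case for a change.** The best case for a change is that the protocol itself makes the absolute claim, so this cannot simply be left to the SAP, and that one sentence would settle it.

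The blinding text does not fully close the gap. The bar in Section 3.5 ends when the primary results are reported, and the OS interim was done at that same analysis. Section 4.2 concerns treatment assignment, not an aggregate OS comparison. By-arm PFS and response were reported from the May 2014 cutoff while that blinding still applied.

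This much stands: the word *strictly* omits the independence condition, and the protocol does not state that the condition was met.

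The rest carries less weight.

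- **Sections 3.5 and 4.2 do not conflict.** One covers aggregate by-arm summaries and the other individual assignment.
- **Table 12 shows its base.** It expresses events as a percentage of the final number and sets 250 at 100%, so a footnote would repeat what is printed.
- **A conditional-error reading cannot be fixed from this document.** It needs the interim z and the original looks, and neither is given.
- **The source is incomplete.** Section 6.9.2 dates the revision to protocol version 5 and a revised SAP. The text at hand is version 8, a safety amendment, so its silence on who decided is weak evidence that nothing was recorded.

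**Conclusion.** No change is needed. The statement on error control is correct if the cut from 385 to 250 deaths was independent of interim OS, and the protocol shows nothing to the contrary. The stated reason is external, assignment stayed blinded until final OS, and no interim OS result is reported. That supports independence without proving it.

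The possible cost is modest for the choice that was actually made: about 0.056 two-sided instead of 0.05, and only for a decision-maker who knew the interim result and optimised on it. The larger bound of 0.045 one-sided requires a free choice over almost any target. With an interim HR above about 0.80, the cut would have made the test stricter.

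The final OS analysis is complete, and its p-value of about 0.0045 lies below every threshold considered. Qualifying the sentence would add a record of provenance but would alter no boundary, analysis or conclusion. The comparisons rest on an interim HR that the protocol does not give and mostly on a single interim in the 385-death plan. The 0.05 claim under independence does not depend on the interim HR.
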